17.1.6 Secondary Outcomes

Table 45: Summary of Secondary Outcome Availability¹ by Site

Study Week	Site 1 (N=XX)	Site 2 (N=XX)	Site 3 (N=XX)	Site 4 (N=XX)	Total (N=XX)
Week 1	N (X.X%)	N (X.X%)	N (X.X%)	N (X.X%)	N (X.X%)
Week 2					
Week 3					
Week 4					
Week 5					
Week 6					
Week 7					
Week 8					
Overall					

¹The secondary outcome is available if there is at least one UDS with a result for the participant's respective primary substance of use (cocaine or methamphetamine). Primary substance of use is designated at randomization. Percentage is calculated as the number of participants with secondary outcome available divided by the number of participants randomized.

Table 46: Summary of Secondary Outcome Availability¹ by Treatment Arm

Study Week	Primary Use Cocaine		Primary Use Methamphetamine		Total (N=XX)	
	Treatment Arm		Treatment Arm			
	Sham (N=XX)	rTMS (N=XX)	Sham (N=XX)	rTMS (N=XX)		
Week 1	N (X.X%)	N (X.X%)	N (X.X%)	N (X.X%)	N (X.X%)	
Week 2						
Week 3						
Week 4						
Week 5						
Week 6						
Week 7						
Week 8						
Overall						

¹The secondary outcome is available if there is at least one UDS with a result for the participant's respective primary substance of use. Primary substance of use is designated at randomization. Percentage is calculated as the number of participants with secondary outcome available divided by the number of participants randomized.

Table 47: Summary of Secondary Outcome Analysis by Treatment Arm

Primary Substance of Use	Treatment Arm	Number of Participants Randomized	Results ²				
			Percentage Negative UDS ¹	Odds Ratio	95% Lower Confidence Limit	95% Upper Confidence Limit	p-value
Cocaine	Sham	N	n/N (XX.X%)	X.XX	X.XX	X.XX	0.xxx
	rTMS						
Methamphetamine	Sham						
	rTMS						

¹ Outcome is defined as the percentage calculated by the number of negative UDS divided by the number total UDS performed; it includes the last UDS per study week over the 8-week treatment period in the participant's primary substance of use assessed at randomization. Missing UDS are not imputed.

² Results are obtained from the treatment arm term of the generalized linear mixed model.

Table 48: Summary of Negative UDS Results¹ by Treatment Arm

Study Week	Primary Use Cocaine ²		Primary Use Methamphetamine ²		Total (N=XX)	
	Treatment Arm		Treatment Arm			
	Sham (N=XX)	rTMS (N=XX)	Sham (N=XX)	rTMS (N=XX)		
Week 1	n/N (X.X%)	n/N (X.X %)	n/N (X.X %)	n/N (X.X %)	n/N (X.X %)	
Week 2						
Week 3						
Week 4						
Week 5						
Week 6						
Week 7						
Week 8						
Overall						

¹ The number of participants with a negative UDS in the participant's respective primary substance of use (cocaine or methamphetamine) on the last UDS administered per study week. Percentage is calculated as the number of participants with a negative UDS divided by the number of participants with a UDS available for that week within the primary substance of use subgroup. Missing UDS are not imputed.

² Primary substance of use is designated at randomization.

17.1.7 Supportive Analyses of the Secondary Outcomes

Table 49: Summary of Secondary Outcome by Sex and Treatment Arm

Primary Substance of Use	Subgroup	Number of Participants Randomized	Treatment Arm		Results ²			
			Sham (N=XX)	rTMS (N=XX)				
			Percentage Negative UDS ¹	Percentage Negative UDS ¹	Odds Ratio	95% Lower Confidence Limit	95% Upper Confidence Limit	p-value
Cocaine	Male	N	n/N (XX.X%)	n/N (XX.X%)	X.XX	X.XX	X.XX	0.xxx
	Female							
Methamphetamine	Male							
	Female							

¹ Outcome is defined as the percentage calculated by the number of negative UDS divided by the number total UDS performed; it includes the last UDS per study week over the 8-week treatment period in the participant's primary substance of use assessed at randomization. Missing UDS are not imputed.

² Results are obtained from the generalized linear mixed model. The odds ratios and p-values result from the treatment arm and subgroup interaction term. Missing UDS are not imputed.

Table 50: Summary of Secondary Outcome by Race and Treatment Arm

Primary Substance of Use	Subgroup	Number of Participants Randomized	Treatment Arm		Results ²			
			Sham (N=XX)	rTMS (N=XX)				
			Percentage Negative UDS ¹	Percentage Negative UDS ¹	Odds Ratio	95% Lower Confidence Limit	95% Upper Confidence Limit	p-value
Cocaine	Black	N	n/N (XX.X%)	n/N (XX.X%)	X.XX	X.XX	X.XX	0.xxx
	White							
	Other ³							
Methamphetamine	Black							
	White							
	Other ³							

¹ Outcome is defined as the percentage calculated by the number of negative UDS divided by the number total UDS performed; it includes the last UDS per study week over the 8-week treatment period in the participant's primary substance of use assessed at randomization. Missing UDS are not imputed.

² Results are obtained from the generalized linear mixed model. The odds ratios and p-values result from the treatment arm and subgroup interaction term.

³ Other includes American Indian or Alaska Native, Native Hawaiian or Pacific Islander, Other, and Multiple Race. Missing or refused responses are not included in the analysis (N=X).

Table 51: Summary of Secondary Outcome by Ethnicity and Treatment Arm

Primary Substance of Use	Subgroup	Number of Participants Randomized	Treatment Arm		Results ²			
			Sham (N=XX)	rTMS (N=XX)				
			Percentage Negative UDS ¹	Percentage Negative UDS ¹	Odds Ratio	95% Lower Confidence Limit	95% Upper Confidence Limit	p-value
Cocaine	Not Hispanic or Latinx	N	n/N (XX.X%)	n/N (XX.X%)	X.XX	X.XX	X.XX	0.xxx
	Hispanic or Latinx							
Methamphetamine	Not Hispanic or Latinx							
	Hispanic or Latinx							

¹ Outcome is defined as the percentage calculated by the number of negative UDS divided by the number total UDS performed; it includes the last UDS per study week over the 8-week treatment period in the participant's primary substance of use assessed at randomization. Missing UDS are not imputed.

² Results are obtained from the generalized linear mixed model. The odds ratios and p-values result from the treatment arm and subgroup interaction term.

Table 52: Summary of Secondary Outcome by Age and Treatment Arm

Primary Substance of Use	Subgroup	Number of Participants Randomized	Treatment Arm		Results ²			
			Sham (N=XX)	rTMS (N=XX)				
			Percentage Negative UDS ¹	Percentage Negative UDS ¹	Odds Ratio	95% Lower Confidence Limit	95% Upper Confidence Limit	p-value
Cocaine	18-44 years	N	n/N (XX.X%)	n/N (XX.X%)	X.XX	X.XX	X.XX	0.xxx
	45 years or greater							
Methamphetamine	18-44 years							
	45 years or greater							

¹ Outcome is defined as the percentage calculated by the number of negative UDS divided by the number total UDS performed; it includes the last UDS per study week over the 8-week treatment period in the participant's primary substance of use assessed at randomization. Missing UDS are not imputed.

² Results are obtained from the generalized linear mixed model. The odds ratios and p-values result from the treatment arm and subgroup interaction term.

Table 53: Summary of Secondary Outcome by Employment Status and Treatment Arm

Primary Substance of Use	Subgroup	Number of Participants Randomized	Treatment Arm		Results ²			
			Sham (N=XX)	rTMS (N=XX)				
			Percentage Negative UDS ¹	Percentage Negative UDS ¹	Odds Ratio	95% Lower Confidence Limit	95% Upper Confidence Limit	p-value
Cocaine	Employed ³	N	n/N (XX.X%)	n/N (XX.X%)	X.XX	X.XX	X.XX	0.xxx
	Unemployed							
	Other ⁴							
Methamphetamine	Employed ³							
	Unemployed							
	Other ⁴							

¹ Outcome is defined as the percentage calculated by the number of negative UDS divided by the number total UDS performed; it includes the last UDS per study week over the 8-week treatment period in the participant's primary substance of use assessed at randomization. Missing UDS are not imputed.

² Results are obtained from the generalized linear mixed model. The odds ratios and p-values result from the treatment arm and subgroup interaction term.

³ Employed includes working now, temporarily laid off, sick leave, or maternity leave.

⁴ Other includes retired, disabled (permanently or temporarily), keeping house, student, and other. Missing or refused responses are not included in the analysis (N=X).

Table 54: Summary of Secondary Outcome Analysis by Major Depressive Episode

Primary Substance of Use	Major Depressive Episode ¹	Number of Participants Randomized	Treatment Arm		Results ³			
			Sham (N=XX)	rTMS (N=XX)				
			Percentage Negative UDS ²	Percentage Negative UDS ²	Odds Ratio	95% Lower Confidence Limit	95% Upper Confidence Limit	p-value
Cocaine	Present	N	n/N (XX.X%)	n/N (XX.X%)	X.XX	X.XX	X.XX	0.xxx
	Absent							
Methamphetamine	Present							
	Absent							

¹ Major Depressive Episode is assessed for current MDE at baseline.

² Outcome is defined as the percentage calculated by the number of negative UDS divided by the number total UDS performed; it includes the last UDS per study week over the 8-week treatment period in the participant's primary substance of use assessed at randomization. Missing UDS are not imputed.

³ Results are obtained from the generalized linear mixed model. The odds ratios and p-values result from the MDE term.

[figure not shown]
Table 55: Summary of Secondary Outcome Analysis by Site

Primary Substance of Use	Site	Number of Participants Randomized	Treatment Arm		Results ³			
			Sham (N=XX)	rTMS (N=XX)				
			Percentage Negative UDS ²	Percentage Negative UDS ²	Odds Ratio	95% Lower Confidence Limit	95% Upper Confidence Limit	p-value
Cocaine	Site 1	N	n/N (XX.X%)	n/N (XX.X%)	X.XX	X.XX	X.XX	0.xxx
	Site 2							
	Site 3							
	Site 4							
Methamphetamine	Site 1							
	Site 2							
	Site 3							
	Site 4							

¹ Outcome is defined as the percentage calculated by the number of negative UDS divided by the number total UDS performed; it includes the last UDS per study week over the 8-week treatment period in the participant's primary substance of use assessed at randomization. Missing UDS are not imputed.

² Results are obtained from the generalized linear mixed model. The odds ratios and p-values result from the site term.

Figure 6: Forest Plot of Secondary Outcome Results

Example figure provided.

Table 56: Summary of Secondary Outcome Analysis: Participant Effect

Primary Substance of Use	Number of Participants Randomized	Within Participant Correlation Results ¹			
		Estimate	Standard Error	95% Lower Confidence Limit	95% Upper Confidence Limit
Cocaine	N	X.XX	X.XX	X.XX	X.XX
Methamphetamine	N				

¹ Results are obtained from the generalized linear mixed model.

Table 57: Summary of Secondary Outcome Analysis: Week by Treatment Arm

Primary Substance of Use	Study Week	Number of Participants Randomized	Treatment Arm		Results ²			
			Sham (N=XX)	rTMS (N=XX)				
			Percentage Negative UDS ¹	Percentage Negative UDS ¹	Odds Ratio	95% Lower Confidence Limit	95% Upper Confidence Limit	p-value
Cocaine	Week 1	N	n/N (XX.X%)	n/N (XX.X%)	X.XX	X.XX	X.XX	0.xxx
	Week 2							
	Week 3							
	Week 4							
	Week 5							
	Week 6							
	Week 7							
	Week 8							
Methamphetamine	Week 1							
	Week 2							
	Week 3							
	Week 4							
	Week 5							
	Week 6							
	Week 7							
	Week 8							

¹ Outcome is defined as the percentage calculated by the number of negative UDS divided by the number total UDS performed; it includes the last UDS per study week over the 8-week treatment period in the participant's primary substance of use assessed at randomization. Missing UDS are not imputed.

² Odds ratio and confidence limit results are obtained from the generalized linear mixed model treatment arm and study week interaction term test for marginal significance. The p-value is obtained from the Type III test for joint significance.

Table 58: Summary of Secondary Outcome Supportive Analyses by Treatment Arm

UDS Results	Treatment Arm	Number of Participants Randomized	Results ²				
			Percentage Negative UDS ¹	Odds Ratio	95% Lower Confidence Limit	95% Upper Confidence Limit	p-value
Negative for all substances ³	Sham	N	n/N (XX.X%)	X.XX	X.XX	X.XX	0.xxx
	rTMS						
Negative for stimulants ⁴	Sham						
	rTMS						
Negative for primary substance of use ⁵	Sham						
	rTMS						

¹ Outcome is defined as the percentage calculated by the number of negative UDS divided by the number total UDS performed; it includes the last UDS per study week over the 8-week treatment period in the participant's primary substance of use assessed at randomization. Missing UDS are not imputed.

² Results are obtained from the treatment arm term of the generalized linear mixed model.

³ Substances include: amphetamine, barbiturate, buprenorphine, benzodiazepines, cocaine, ecstasy, fentanyl, marijuana, methamphetamine, methadone, opiates, oxycodone, and phencyclidine.

⁴ Substances include: amphetamine, cocaine, and methamphetamine.

⁵ Primary substance of use (cocaine or methamphetamine) is assessed at randomization.

Table 59: Summary of Negative UDS Results in Participants with rTMS Session Threshold Met¹ by Treatment Arm

Primary Substance of Use	Treatment Arm	Number of Participants with Threshold Met	Results ³				
			Percentage Negative UDS ²	Odds Ratio	95% Lower Confidence Limit	95% Upper Confidence Limit	p-value
Cocaine	Sham	N	n/N (XX.X%)	X.XX	X.XX	X.XX	0.xxx
	rTMS						
Methamphetamine	Sham						
	rTMS						
Overall	Sham						
	rTMS						

¹ Participants met the rTMS session threshold if they completed at least 20 rTMS sessions.

² Outcome is defined as the percentage calculated by the number of negative UDS divided by the number total UDS performed; it includes the last UDS per study week over the 8-week treatment period in the participant's primary substance of use assessed at randomization. Missing UDS are not imputed.

³ Results are obtained from the treatment arm term of the generalized linear mixed model.

Table 60: Summary of Secondary Outcome Sensitivity Analysis by Treatment Arm

Method	Results	N	Odds Ratio	95% Lower Confidence Limit	95% Upper Confidence Limit	p-value
Protocol defined secondary outcome	Secondary outcome (missing UDS not imputed)	N	X.XX	X.XX	X.XX	0.xxx
Sensitivity analysis: Time	Study Week defined as strict 7-day window					
	Time defined using Study Day					
Imputation of missing UDS	Missing UDS imputed as negative					
	Missing UDS imputed as positive					
	Missing UDS imputed based on self-reported use (TLFB)					
	Multiple imputation					

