7.6 Supportive Analyses of the Secondary Outcome Measures

7.6.1 Demographic Subgroup Analyses

The secondary (efficacy) outcome results will be presented and tested within each demographic subgroup described in Section 7.3.1 by including interactions with treatment assignment in the model. Summaries will include the odds ratio, confidence interval, and p-value similar to the secondary outcome, including a forest plot. The corresponding SAS code is provided below:

```
proc glimmix data = data method = quad;
  class site week participant;
  model y(event = '1') = trt|subgroup mde week site /
    dist = binary link = logit solution;
  random intercept / subject = participant;
run;
```

where:

- data is a dataset with one row per weekly UDS per participant for the specified primary substance of use,
- y is the binary variable with a value of 1 indicating the UDS for that participant was negative and 0 indicating positive UDS result,
- trt is a binary variable with a value of 1 indicating active rTMS and 0 indicating sham rTMS,
- subgroup is the demographic variable of interest,
- mde is a binary variable with a value of 1 indicating the presence of MDE,
- week is the study week (1 – 8, categorical),
- site is a categorical variable containing which of the sites each participant was enrolled in, and
- participant is the participant ID.

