7.10.1 Secondary Outcome Analyses

The following changes to the analysis plan for the secondary outcome measure, including the main analysis, demographic subgroup analyses, and supportive analyses, were presented by DSC statisticians to the Lead Node on 02OCT2024. During this presentation, limited summary statistics were presented to the LN to illustrate the issues encountered during analysis. This included three redacted summary tables with masked treatment arm and subgroup names. Note that no results were presented; percentages only (no counts) were used, and no measures of significance were shown. The Lead Investigator and LN statisticians reviewed and made decisions regarding alternative modelling approaches to consider given the lack of variability and parameter space boundary issues. Thus, the additional analytic method decisions were made by parties that had not been privy to any unblinded information regarding the secondary outcome that could possibly impact their determination.

The general approach to dealing with models specified in version 1.0 of the SAP that produced unreliable results is as follows. If the original generalized linear mixed model including fixed effects for treatment, major depressive episode (MDE), week, and site and a random effect for participant converges and produces reliable results, the model will be used and results reported, as pre-specified in the initial version of the SAP. If that model does not converge or produce reliable results (e.g. an OR confidence interval limit over 50), a simplified model will be attempted. The simplified model will include a fixed effect for treatment arm and a random effect for participant. If the simplified model does not converge or produce reliable results, only the summary statistics for percentage negative UDS by primary substance of use, treatment arm, and subgroup (as applicable) will be presented.

If the model does not converge or produce reliable results due only to no variability in a subgroup, results will be presented within the other levels of the subgroup. This may occur if there are no participants in one treatment arm of a subgroup or all participants in that subgroup have no positive UDS results. No p-value will be reported as there is no planned test for significance between treatment arm and subgroup.

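### The footnotes to SAP Tables 49–53 and 57 take each row's odds ratio from the interaction term, which is a ratio of odds ratios and not the rTMS-versus-sham effect within that level

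*SAP*

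**What the plan says.** **Text.** SAP Section 7.6.1 says that the secondary outcome results "will be presented and tested within each demographic subgroup described in Section 7.3.1 by including interactions with treatment assignment in the model". Its code has the statement "model y(event = '1') = trt|subgroup mde week site" with "class site week participant" as the class variables. Neither treatment nor subgroup is a class variable. The code prints the coefficient solution and contains no ESTIMATE, LSMEANS or SLICE statement. Section 7.6.2, item 1, sends the treatment-by-week analysis to the same code and allows treatment effects by week to be shown if the interaction is significant.

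Section 7.10.1, added in version 2.0, covers a model that fails only because one subgroup level has no variability. Results are then given within the remaining levels, and the paragraph ends: "No p-value will be reported as there is no planned test for significance between treatment arm and subgroup". Section 9.0 says that, apart from the treatment test, no hypothesis test is planned on the primary or secondary outcomes.

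**Shells (Section 17.1.7).** Tables 49–53 have one row per subgroup level, with the sham and rTMS percentages, an odds ratio, its limits and a p-value. Footnote 2 of each reads "The odds ratios and p-values result from the treatment arm and subgroup interaction term". Table 57 has eight week rows per use disorder. Its footnote 2 reads "Odds ratio and confidence limit results are obtained from the generalized linear mixed model treatment arm and study week interaction term test for marginal significance", followed by "The p-value is obtained from the Type III test for joint significance".

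**For comparison.** Section 7.5 takes the main odds ratio from the exponentiated treatment coefficient, and the Table 47 footnote names the treatment term.

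**The concern.** A row labelled Female, or Week 3, beside the sham and rTMS percentages for that level, will be read as the rTMS-versus-sham odds ratio in that level. The footnotes name something else: a comparison of that level's effect with the effect in a reference level. A programmer who follows them would put a ratio of odds ratios under a treatment-effect label, in the tables and in the forest plot that Section 7.6.1 requires.

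Two misreadings could follow. A benefit shared by all levels would tend to look like no effect. A level with no effect could look like benefit or harm, depending on the reference level. The study is meant to inform the design of later trials, so subgroup and week patterns may be carried forward.

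**Working it through.** The shells are empty, so the plan has no figure of its own to reproduce here.

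**1. What the interaction term is.** Leaving out MDE, week, site and the random intercept, the model for a two-level subgroup is

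logit(p) = b0 + b1·trt + b2·sub + b3·trt·sub

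- odds ratio in the reference level: exp(b1)
- odds ratio in the other level: exp(b1 + b3)
- interaction term: exp(b3) = odds ratio in the other level ÷ odds ratio in the reference level

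**2. Coefficients against rows.** A factor with k levels has k − 1 interaction coefficients: 2 − 1 = 1 for two rows, and 8 − 1 = 7 for eight weeks. The reference row has no estimate, or a fixed 1.00 with no confidence interval. Because subgroup is not a class variable, a three-level factor coded as a number would give one coefficient for three rows. Section 7.10.1 now collapses race and employment to two levels, but Tables 50 and 53 still show three.

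**3. Numerical check.** Inputs from SAP Section 10.2: sham probability of a negative UDS 0.36, 8 UDS per participant, 80 participants per use disorder, ICC 0.25. The random-intercept SD is sqrt(0.25/0.75 × π²/3) = 1.047, which matches the stated 1.05. Assumptions: two equal subgroup levels and no site, week or MDE covariates. Medians over 300 simulated trials:

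| True OR, reference / other | exp(b1) | exp(b1 + b3) | exp(b3), the interaction term |
|---|---|---|---|
| 1 / 1 | 0.99 | 1.03 | 1.01 |
| 2 / 2 | 2.02 | 2.06 | 1.02 |
| 4 / 4 | 4.12 | 3.95 | 1.00 |
| 0.5 / 1 | 0.49 | 1.00 | 2.04 |
| 3 / 1.5 | 3.12 | 1.52 | 0.51 |

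The first three rows cannot be told apart from the interaction term. In the fourth, a level with no effect would show about 2. In the fifth, a level with a true odds ratio of 1.5 would show about 0.5.

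As a check on the simulation, power at N = 80 and p = 0.36 (1,000 replicates) was compared with Protocol Table 8: 96.4% against 96% (ICC 0.25, OR 3), 86.4% against 86% (ICC 0.5, OR 4), 64.7% against 67% (ICC 0.25, OR 2) and 31.2% against 35% (ICC 0.5, OR 2). The last two differ by more than 2 points. The point here rests on step 1 and not on these power values.

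**4. Scatter in one trial.** The standard error of b3 was about 0.57. Around a true ratio of 1, 95% of estimates fall between exp(−1.96 × 0.57) = 0.33 and exp(1.96 × 0.57) = 3.06. Only 27% to 32% of simulated values lay within 0.80–1.25 in the three uniform-effect rows.

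**5. Week.** In one large simulated dataset each (N = 2,000), the seven interaction terms ran from 0.76 to 1.09 for a constant odds ratio of 2, and from 0.92 to 1.18 for a constant 4. The within-week contrasts ran from 1.54 to 2.21 and from 3.40 to 4.35.

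As a hypothetical case in which the interaction is real, let the weekly odds ratio rise evenly from 1.0 to 3.0, with week 8 as reference. Dividing each by 3.0 gives 0.33, 0.43, 0.52, 0.62, 0.71, 0.81 and 0.90 for weeks 1–7, so weeks with no effect or a benefit would appear as harm.

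**6. The p-value rule.** Section 7.6.1 has the subgroup results tested, and the footnotes to Tables 49–53 take the p-values from the interaction. The closing sentence of Section 7.10.1 says that no such test is planned, and Section 9.0 allows for none. For week, Section 7.6.2 and Table 57 agree on one joint Type III test.

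**The case against.** The strongest reply is that the footnotes are loose shorthand for level-specific effects taken from the interaction model. The body text supports this intent. The Section 7.10.1 rule on presenting the remaining levels makes sense only for within-level odds ratios, because with two levels a ratio cannot be formed once one level has no variability. The SAP's code is also abbreviated elsewhere: the main model in Section 7.5 requests neither exponentiation nor confidence limits, yet both are to be reported.

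The intent stands, but the shorthand reading is weak. Neighbouring footnotes name specific terms and mean them: the treatment term (Table 47), the MDE term (Table 54) and the site term (Table 55). The imputation code in Section 7.9 does include an ESTIMATE statement with exponentiation where a contrast is wanted.

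Four stronger readings are tempting, and the documents do not support them:

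- A reader might infer that the SAP has adopted the ratio as its subgroup effect. It has not; the footnotes conflict with the text.
- A reader might infer that every row would print about 1.0 under a uniform effect. That holds for the centre of the distribution only. The reference row has no estimate, and single-trial values scatter as in step 4.
- A reader might apply the same picture to Table 57 under a constant weekly effect. Section 7.6.2 shows weekly estimates only if the interaction is significant. With a constant effect, that would happen in about 5% of trials, assuming a 0.05 level.
- A reader might infer that Section 7.10.1 withdraws all subgroup p-values. The sentence closes the paragraph on the no-variability fallback. Only the reason it gives is general, and that is what clashes with Section 7.6.1.

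Two mitigating facts also stand. The percentages by arm are printed beside each odds ratio, so a mismatch could be noticed. And Section 7.10 records that the planned models gave unreliable estimates after database lock; its fallback is a model with treatment and a participant effect only, then summary statistics. Some interaction odds ratios may therefore never be produced.

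**Conclusion.** The footnotes to Tables 49–53 and 57 are wrong as written. They name a quantity that is not the within-level rTMS-versus-sham odds ratio and that leaves the reference row without an estimate. They conflict with Sections 7.6.1, 7.6.2 and 7.10.1 and with the row layout.

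The error can be as large as the effect itself: a uniform odds ratio of 2 or of 4 gives an interaction term centred on 1. This follows from the algebra and needs no assumption about the data. The simulated medians and the standard error of 0.57 do rest on the SAP's power inputs at ICC 0.25, equal subgroup sizes and 80 participants per use disorder; smaller groups would scatter more.

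The reach is limited. These are supportive analyses, Table 47 uses the treatment term and is unaffected, and the documents do not show which quantity was actually printed. The correction should be made, but the main secondary result does not depend on it.

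**What to change.** 1. In Section 7.6.1 and Section 7.6.2 item 1, define each row as the rTMS-versus-sham odds ratio and 95% CI within that level, exp(b1) for the reference level and exp(b1 + b3) for another. Obtain it by ESTIMATE statements with exponentiation and confidence limits, or by LSMEANS or slice differences. The LSMEANS route needs both `trt` and `subgroup` in CLASS; adding only the subgroup is not enough.
2. Reword footnote 2 of Tables 49–53 and of Table 57 to match.
3. Report one Type III interaction p-value per factor, as Table 57 already does for week, or none. Make Section 7.6.1, the closing sentence on planned tests in Section 7.10.1, and Section 9.0 agree.
4. Bring the three-level rows of Tables 50 and 53 into line with the two levels in Section 7.10.1.
5. If the tables have already been produced, check which quantity was printed, and correct the rows or their labels.

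The cost is a few lines of SAS and some footnote wording, with no new data. The change corrects the quantity shown; the within-level estimates will still be imprecise.
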